6.13.2.1. Common Adverse Events

The percentages of patients with TEAEs will be summarized by treatment using MedDRA PT for the common TEAEs (occurred in $\geq 1\%$ before rounding of treated patients). Events will be ordered by decreasing frequency in the all miri group. See [Table AMAK.6.7](#) and [Figure AMAK.6.2](#).

6.13.3. Deaths, Other Serious Adverse Events, and Other Notable Adverse Events

The number and percentage of patients who reported a serious adverse event (SAE) during the treatment period will be summarized by treatment using MedDRA PT nested within SOC. Events will be ordered by decreasing frequency in the all miri group within SOC. This analysis will be conducted for all 3 safety populations. A listing of SAEs will be provided.

The number and percentage of patients who permanently discontinued from study treatment due to an AE (including AEs that led to death) during the treatment period will be summarized by treatment using MedDRA PT nested within SOC. Events will be ordered by decreasing frequency in the all miri group within SOC. This analysis will be conducted for all 3 safety populations.

6.13.4. Clinical Laboratory Evaluation

As described more fully in compound level safety standards and in the laboratory-related PhUSE white papers (PhUSE 2013; PhUSE 2015), the clinical laboratory evaluations will be summarized with the following displays described in [Table AMAK.6.8](#).

Table AMAK.6.8. Summaries/Displays/Analysis for Clinical Laboratory Evaluations

Analysis	Population/ Period ^a
Box plots of observed values (and change from baseline values) by visit. Change from baseline to last observation will be summarized within the box plot of changes (rightmost column), and descriptive summary statistics will be included in a table below the	I; R

box plot along with a p-value using the ANCOVA model described in Section 6.13.	
Treatment-emergent abnormal high lab values (i.e., patients shifting from a normal/low maximum baseline value to a high maximum postbaseline value) or low laboratory values (i.e., patients shifting from normal/high minimum baseline value to a low minimum postbaseline value).	I; R; A
Scatter plot of maximum (minimum) postbaseline value versus maximum (minimum) baseline value.	I; R
Shift tables showing the number of patients who shift from each category of maximum (minimum) baseline observation to each category of maximum (minimum) postbaseline observation. Here, categories may be low, normal, or high with cut-offs defined in the compound level safety standards.	I; R

Abbreviation: ANCOVA = analysis of covariance.

^a Populations are abbreviated as follows: I = Induction Safety; R = Re-randomized Maintenance Safety; A = All Miri Safety.

For these displays, the postbaseline periods will be identical to those described in Section 6.13.2. Postbaseline measurement for continuous analysis (e.g., boxplots) will include *only* scheduled measurements, while postbaseline categorical analysis (e.g., shifts) will include *both* scheduled and unscheduled measurements.

Measurements are defined to be in the baseline periods as follows:

- *Induction Safety Population:*
 - For analyses of continuous measurements: the last scheduled or unscheduled non-missing measurement recorded during the screening period.
 - For analyses of categorical measurements: all scheduled or unscheduled non-missing measurements recorded during the Screening Period.
- *Re-randomized Maintenance Safety Population:*
 - For analyses of continuous and categorical measurements: the last scheduled or unscheduled non-missing measurement recorded during the Induction Period (i.e., the baseline period only includes a single assessment).
- *All Miri Safety Population:*
 - For analyses of continuous measurements: (1) the last scheduled or unscheduled non-missing measurement recorded during the Screening Period for the patients randomized to miri during induction; (2) the last scheduled or unscheduled non-missing measurement recorded before first miri treatment for all other patients.
 - For analyses of categorical measurements: (1) all scheduled or unscheduled non-missing measurements recorded during the Screening Period for the patients randomized to miri during induction, (2) the last scheduled or unscheduled non-missing measurement recorded before first miri treatment for all other patients.

For any laboratory test given on the day of first taking study medication at the start of the postbaseline period, the start time of the study treatment will be used to determine whether the laboratory test was pre- versus postbaseline. If time for the laboratory test is missing, it will be assumed to be in the baseline period (i.e., assume the protocol-defined order of procedures was

followed). Following the compound-level safety standards, for some laboratory tests, a safety concern may exist for only high (or only low) values. For these laboratory tests, displays with only maximum (or minimum) values will be used and shift tables will be presented accordingly.

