EQ-5D-5L-PSO		X			X		X			X			X			X	X			
TSQM		X					X			X			X			X	X			
Laboratory Tests																				
Hematology ^l	X	X	X	X	X		X		X		X		X		X	X	X		X	
Clinical Serum Chemistry ^l	X	X	X	X	X		X		X		X		X		X	X	X		X	

Procedure ^a	Screening Period	Baseline	Induction Period					Maintenance Period									ETVs	Follow-up Period ^t	
			V 3	V 4	V 5	V 6	V 7	V 8	V 9	V 10	V 11	V 12	V 13	V 14	V 15	V 16		V 801	V 802
Visit Number	V 1 ^b	V 2	V 3	V 4	V 5	V 6	V 7	V 8	V 9	V 10	V 11	V 12	V 13	V 14	V 15	V 16		V 801	V 802
Week	-4	0	2	4	8	12	16	20	24	28	32	36	40	44	48	52		LV +4W	LV +12W
Day with Visit Tolerance Interval	≤28 days from V2	1	15 ± 3	29 ± 3	57 ± 5	85 ± 5	113 ± 5	141 ± 5	169 ± 5	197 ± 5	225 ± 5	253 ± 5	281 ± 5	309 ± 5	337 ± 5	365 ± 5		29 ± 5	85 ± 5
Lipid Panel (fasting) ^m		X					X									X			
Urinalysis	X	X					X										X ^u		
hsCRP		X		X	X		X		X		X		X			X			
HBsAg, HBcAb, HBsAb	X ⁿ																		
HBV DNA testing ⁿ	X					X			X			X			X		X	X	X
Hepatitis C Antibody	X																		
HCV RNA testing	X	X ^o	X ^o	X ^o	X ^o	X ^o	X ^o	X ^o	X ^o	X ^o	X ^o	X ^o	X ^o	X ^o	X ^o	X ^o	X ^o		X ^o
HIV	X																		
Immuno-genicity for miri P		X	X	X	X		X	X	X		X		X			X	X		X
Serum for miri conc (PK) ^q		X	X	X	X		X	X	X		X		X			X	X		X
Serum Pregnancy Test (WCBP only)	X																		

Procedure ^a	Screening Period	Baseline	Induction Period					Maintenance Period									ETV ^s	Follow-up Period ^t		
			V 3	V 4	V 5	V 6	V 7	V 8	V 9	V 10	V 11	V 12	V 13	V 14	V 15	V 16		V 801	V 802	
Visit Number	V 1 ^b	V 2	V 3	V 4	V 5	V 6	V 7	V 8	V 9	V 10	V 11	V 12	V 13	V 14	V 15	V 16		V 801	V 802	
Week	-4	0	2	4	8	12	16	20	24	28	32	36	40	44	48	52		LV +4W	LV +12W	
Day with Visit Tolerance Interval	≤28 days from V2	1	15 ±3	29 ±3	57 ±5	85 ±5	113 ±5	141 ±5	169 ±5	197 ±5	225 ±5	253 ±5	281 ±5	309 ±5	337 ±5	365 ±5		29 ±5	85 ±5	
Urine Pregnancy Test (local; WCBP only)		X		X	X	X	X	X	X	X	X	X	X	X	X	X	X	X	X	X
FSH	X ^r																			
Serum/Plasma for Storage/CCI		X			X		X									X	X		X	
Serum/Plasma for Storage/CCI		X	X	X	X		X		X		X		X		X	X	X		X	
CCI		X			X		X									X	X		X	
Blood for DNA Pharmacogenetics		X																		

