- d Sitting blood pressure, temperature, and pulse will be obtained within approximately the same time frame as ECG measurements or blood sampling. When multiple assessments are scheduled for the same time point, the preferred order of completion should be as follows: ECG (if applicable), vital signs, and then blood sampling.
- e Chest radiography will be performed locally at screening unless it has been performed within 3 months before initial screening (provided the radiographs and/or formal report are available for the investigator’s review). For additional details, see Section 9.4.5.3.
- f TB testing will be performed at screening unless it has been performed within 3 months before initial screening (provided the formal report is available for the investigator’s review). It may also be performed after screening if clinically indicated. TB testing will be performed locally using an interferon- γ release assay (IGRA; QuantiFERON[®]-TB Gold or T-SPOT.TB[®]) or a purified protein derivative (PPD) tuberculin skin test. If PPD test is performed, patients will return 2 to 3 days afterwards to have their PPD test read. For additional details on TB testing, see Exclusion Criterion [19] and Section 9.4.5.2.
- g The preferred order of completion is supine ECG prior to vital signs, blood sampling, or any other study procedures. For additional details on ECG collection, see Section 9.4.1. ECG should be performed at the ETV and Visit 802 only if there is early termination due to a cardiovascular event.
- h A Self-Harm Follow-Up Form is to be completed only during visits for which there is at least 1 discrete self-harm event identified on the Self-Harm Supplement Form (see Section 9.2.2).
- i PSSI, NAPSI, and PPASI assessments are applicable only if symptoms are present at baseline.
- j These assessments should be completed before administration of investigational product, before the patient’s clinical examination, before the patient receives any tests or results, and before the patient’s health, health data, or emotions are discussed.
- k Electronic diaries will be distributed at the screening visit and collected at the Week 16 visit.
- l Unscheduled hematology or blood chemistry panels may be performed at the discretion of the investigator.
- m Patients should not eat or drink anything except water for 12 hours prior to sample collection.

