Appendix 2. Clinical Laboratory Tests

Clinical Laboratory Tests

Hematology^a	Clinical (Serum) Chemistry^a	Other
Hemoglobin	Serum Concentrations of:	Human immunodeficiency virus (HIV) ^b
Hematocrit	Sodium	Hepatitis B surface antigen (HBsAg) ^b
Erythrocyte count (RBC)	Potassium	Hepatitis B core antibody (HBcAb) ^b
Mean cell volume	Total bilirubin	Hepatitis B surface antibody (HBsAb) ^b
Mean cell hemoglobin	Total protein	HBV DNA test ^c
Mean cell hemoglobin concentration	Direct bilirubin	Hepatitis C antibody ^b
Leukocytes (WBC)	Alkaline phosphatase (ALP)	HCV RNA test ^e
Cell morphology	Alanine aminotransferase (ALT)	Pregnancy Test (females only)
Absolute Counts and Percentage of:	Aspartate aminotransferase (AST)	Serum ^b
Neutrophils, segmented	Gamma-glutamyl transferase (GGT)	Urine (assayed locally by clinical study site)
Lymphocytes	Blood urea nitrogen (BUN)	Follicle-stimulating hormone (FSH) ^b
Monocytes	Creatinine	PPD or QuantiFERON-TB Gold test or T-SPOT.TB test ^d
Eosinophils	Uric acid	Exploratory storage samples (DNA)
Basophils	Calcium	Exploratory storage samples (serum, plasma, whole blood, RNA)
Absolute Counts of:	Glucose	Anti-mirikizumab antibodies (immunogenicity) ^a
Platelets	Albumin	Serum mirikizumab concentration (PK) ^a
	Cholesterol (total)	Tryptase ^a
	Triglycerides	Complement panel (C3 and C4) ^a

Urinalysis	Creatine kinase (CK)	Cytokine panel ^a
Specific gravity		High-sensitivity C-reactive protein (hsCRP)
pH	Lipid Panel (fasting)	
Protein	Low-density lipoprotein (LDL)	
Glucose	High-density lipoprotein (HDL)	
Ketones	Very-low-density lipoprotein (VLDL)	
Bilirubin		
Urobilinogen		
Blood		
Nitrite		
Urine leukocyte esterase		
Microscopic examination of sediment		

Abbreviations: DNA = deoxyribonucleic acid; HBV = hepatitis B virus; HCV = hepatitis C virus;

PK = pharmacokinetic(s); PPD = purified protein derivative (skin test); RBC = red blood cells;

RNA = ribonucleic acid; TB = tuberculosis; WBC = white blood cells.

- a. Unscheduled hematology or blood chemistry panels may be performed at the discretion of the investigator. If a patient develops an acute hypersensitivity event after administration of IP, blood samples will be collected for pharmacokinetic, immunogenicity, and exploratory hypersensitivity analyses.
- b. Performed at screening only.

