6.1.2. Study Time Intervals

Table AMAK.6.3 displays a list of study periods along with the definition of which patients will be considered to have entered the study period and when the individuals start and end the study period. The table shows both a date and a time.

To calculate the length of any time interval or time period in this study, the following formula will be used:

$$\text{Length of interval (days)} = \text{End Date} - \text{Interval Start Date} + 1$$

To convert any time length from days to years, the following formula will be used:

$$\text{Length of interval (years)} = \text{Length of interval (days)} / 365.25$$

To convert any time length from days to weeks, the following formula will be used:

$$\text{Length of interval (weeks)} = \text{Length of interval (days)} / 7$$

Only for the purpose of calculating the length of study period time intervals, the words “prior to” in [Table AMAK.6.3](#) should be understood to mean “the day before,” while the word “after” should be understood to mean “the day after.”

Table AMAK.6.3. Definition of Study Period Time Intervals

Study Period	Start Definition	End Definition
Screening: All patients who sign informed consent are considered as entering the Screening Period.	Informed consent date	Prior to the start of induction.
Induction Period Interval: All patients who are randomized to the study are considered as entering the Induction Period.	At the first injection date/time ^a following randomization. For patients who are randomized but not dosed, the Induction Period starts on the date of randomization.	Prior to the start of maintenance. For patients who discontinue before or on the Week 16 visit, the induction period ends at the last date of treatment discontinued date or last treatment visit date.
Maintenance Period Interval: All patients who had any Week 16 to Week 52 visits (except the ones who discontinued the study at Week 16) are considered to have entered the Maintenance Period.	At the Week 16 dosing date/time ^a . If a patient is unable to be dosed at the Week 16 visit, the Maintenance Period starts at the Week 16 visit. If the patient misses the Week 16 visit, the Maintenance Period starts at Day 118.	After the Week 52 visit date. If patients discontinued prior to Week 52, the Maintenance Period ends at the last date of treatment disposition date or last treatment visit date. If the patient relapsed, the Maintenance Period ends before the patient entered the relapse period.

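### In maintenance, the tested change to last observation for triglycerides, glucose and total cholesterol mixes draws with and without a fasting requirement, and relapse decides which kind a patient contributes

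*SAP*

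**What the plan says.** - **Analytes.** Protocol Appendix 2 lists total cholesterol, "Triglycerides" and glucose under serum chemistry. LDL, HDL and VLDL come under a separate fasting lipid panel heading.
- **Visits.** In the Schedule of Activities, the row "Clinical Serum Chemistry ^l" is marked at V1 to V5, V7, V9, V11, V13, V15, V16, the early termination visit and V802. Its footnote concerns unscheduled panels only. The row "Lipid Panel (fasting) ^m" is marked at V2, V7 and V16 (Weeks 0, 16 and 52). Its footnote reads: "Patients should not eat or drink anything except water for 12 hours prior to sample collection".
- **Analysis.** SAP 6.13.4, Table AMAK.6.8: "Change from baseline to last observation will be summarized within the box plot of changes (rightmost column", with a p-value, for the Induction Safety and Re-randomized Maintenance Safety populations. The ANCOVA in SAP 6.13 contains treatment and baseline only. Postbaseline values for continuous analyses are limited to scheduled measurements. Fasting state is not mentioned.
- **Maintenance window.** Baseline is the last non-missing value in the Induction Period (SAP 6.13.4). On its end, SAP Table AMAK.6.3 says: "If the patient relapsed, the Maintenance Period ends before the patient entered the relapse period".
- **Comparison.** SAP Table AMAK.6.2 lists each mirikizumab dose against placebo as an inferential comparison in the Re-randomized Maintenance Safety population.

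**The concern.** A last-observation analysis assumes that the last value is collected under comparable conditions in all arms. Here the conditions depend on the visit at which a patient's window closes. That depends on relapse, which randomised withdrawal is designed to provoke on placebo. The treatment contrast for these three analytes can therefore contain a difference in fasting state as well as any drug effect. The unfavourable direction for a safety display is that a higher placebo mean hides a metabolic rise on mirikizumab.

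**Working it through.** **Background figure.** Maintenance arm size is 400 × 0.70 / 3 = 93.3, which matches the stated 93 or so. Power at two-sided 0.025 for 80% or 70% against 10% is above 0.999, consistent with the stated >95%. Neither figure is in dispute.

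**Step 1: fasting status of the draws.** Of the 11 scheduled chemistry visits from V1 to V16, 3 (V2, V7, V16) coincide with the fasting panel and 8 do not. Of the 5 postbaseline maintenance visits, 4 (V9, V11, V13, V15) carry no fasting requirement. The early termination visit has none either.

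**Step 2: last chemistry draw by relapse visit.** Schedule footnote a puts assessments before dosing, and the Relapse Period starts at the first dose after relapse is measured. The draw at the relapse visit therefore counts as maintenance.

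| Relapse first seen at | Last maintenance chemistry | Fast required? |
|---|---|---|
| V8 | none | – |
| V9, V10 | V9 (Week 24) | no |
| V11, V12 | V11 (Week 32) | no |
| V13, V14 | V13 (Week 40) | no |
| V15 | V15 (Week 48) | no |
| V16, or no relapse and completed | V16 (Week 52) | yes |

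If the relapse-visit draw were excluded, patients relapsing at V9 would have no value. The other last draws up to V15 would stay the same or move one chemistry visit earlier, still without a fasting requirement.

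Patients relapsing at V9 to V15 thus contribute a no-fast value minus a fasting value. Non-relapsing completers contribute fasting minus fasting.

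**Step 3: does relapse differ by arm?** The documents give no relapse rate. SAP 5.1 assumes PASI 90 is maintained in 80% (250 mg), 70% (125 mg) and 10% (placebo). Under SAP 6.3.1 a relapsed patient is a non-responder at later visits. The planning assumptions therefore cap relapse at about 1 − 0.80 = 20%, 1 − 0.70 = 30% and 1 − 0.10 = 90%. These are upper guides, but the direction is clear.

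**Step 4: size, under assumed inputs.** Bias in the placebo-minus-mirikizumab difference = s × f × (qP − qM). Here s is the non-fasting shift and f is the share of no-fast draws that were really non-fasting. The terms qP and qM are the shares, among patients with a postbaseline value, whose last draw is a no-fast one.

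*Triglycerides.* Assume s = 0.2 to 0.5 mmol/L, qP = 50 to 70%, qM = 10%, SD of change 0.8 mmol/L and 93 per arm.
- f = 1: 0.2 × 0.4 = 0.08, up to 0.5 × 0.6 = 0.30 mmol/L.
- SE = 0.8 × √(2/93) = 0.117, so the bias is 0.7 to 2.6 SE.
- f = 0.5: 0.04 to 0.15 mmol/L, or 0.3 to 1.3 SE.

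*False-positive rate at nominal 5% with no drug effect.* This is a simulation of the SAP ANCOVA: 93 per arm, 3,000 runs, f = 1, s in SDs of a single measurement, and assumed baseline correlation 0.6.

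| qP / qM | s = 0 | 0.1 | 0.25 | 0.5 |
|---|---|---|---|---|
| 90% / 20% | 5.5% | 8.6% | 30.8% | 82.7% |
| 50% / 5% | – | – | 15.9% | 45.4% |
| 20% / 20% | – | – | – | 3.9% |

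At the mild end, a normal approximation with 30% against 20% and s of 0.1 to 0.5 SDs of change gives 5.1% to 6.3%, which is negligible. Inflation needs both a fasting shift and unequal relapse.

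**The case against.** - **Unseen document.** SAP 6.13.4 defers detail to compound level safety standards that are not supplied. A fasting rule could sit there. This stands, and the fix allows for it.
- **No requirement is not proof of eating.** This also stands. It is why f appears in the formula, and why the upper figures in the working are not estimates.
- **Not all relapsers count.** Relapse at V8 gives no postbaseline chemistry, and relapse first seen at V16 ends on a fasting draw. Early discontinuers in any arm may end on an early termination draw without a fast. All three change qP − qM by unknown amounts.
- **Low consequence.** Protocol 10.3.4 plans only summaries by treatment for maintenance safety. The p-value comes from the SAP, lies outside the multiplicity scheme, and may not reach the study report. Like-for-like displays exist: box plots of change by visit, and LDL, HDL and VLDL drawn only at fasting visits. This limits the importance of the problem but does not remove it, because the SAP still plans a test that cannot be read cleanly.
- **Induction.** A reader might infer that induction is biased too, since Weeks 2, 4 and 8 carry no fast while Week 0 does. The documents do not support that for the treatment contrast: both arms follow the same rule at each visit, and Weeks 0 and 16 are both fasting visits. A rise shared by both arms could appear in the by-visit plots. The induction last observation is exposed only through early discontinuers.

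**Conclusion.** The structural point holds on the documents alone. For these three analytes, the tested maintenance change to last observation compares values collected under different fasting rules, and relapse decides which rule applies.

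The direction rests on two expectations: more relapse on placebo, which the planning assumptions support, and higher non-fasting values. The second is most plausible for triglycerides and glucose and least secure for total cholesterol; the documents give no food effect for any of them. The size cannot be computed. The range of 0.04 to 0.30 mmol/L is for triglycerides only and depends wholly on assumed inputs.

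A reader might go further and infer that the maintenance laboratory comparison is confounded throughout, or that a mirikizumab effect would be hidden. Neither follows. This is differential measurement after randomisation in one summary of three analytes, and contrasts between arms at a given visit are not biased by it. It is worth correcting because the change is cheap, but no efficacy conclusion depends on it.

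**What to change.** In SAP 6.13.4, for triglycerides, glucose and total cholesterol:

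1. Flag each draw by whether its visit required fasting.
2. Report the mixed change to last observation descriptively, without a p-value.
3. Base any test on matched visits. Use Week 16 to Week 52 as the fasting comparison, stating that it covers only patients still in the Maintenance Period. Compare other visits one at a time.
4. Keep all scheduled and unscheduled draws in the treatment-emergent high/low and shift displays, with the flag shown.
5. If the compound level safety standards already contain a fasting rule, cross-reference it instead.

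Restricting every analysis to Weeks 0, 16 and 52 is tempting but costs more. It would condition the maintenance comparison on not having relapsed, and would discard Week 24 to 48 and early termination safety values.

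The cost of the recommended change is SAP wording and the loss of the single tested last-observation summary for these three analytes. No new data are needed.

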6.13.5. Vital Signs and Other Physical Findings

As described more fully in compound level safety standards and in the vital signs-related PhUSE white papers (PhUSE 2013; PhUSE 2015), vital signs will be summarized similarly to the clinical laboratory evaluation (see Section 6.13.4). For vital signs, the low and high limits are based on a combination of a specified value and a change or percentage change. In this case, the PhUSE white paper recommends providing scatter plots and shifts to low/high. Boxplots will also be presented.

6.13.6. Electrocardiograms

Complete electrocardiogram (ECG) data will not be part of the clinical database for the individual studies. Any clinically significant findings from ECGs that result in a diagnosis and that occur after the patient receives the first dose of the investigational treatment will be reported to Lilly or its designee as an AE via eCRF. Aside from standard AE summary tables, no additional analysis of ECG data will be performed.

